2.3 Visit Schedule and Study Assessment

The flow chart of visit schedule and study assessments is given in Appendix A of the Study Protocol.

3 STATISTICAL METHODS

3.1 General Methods

3.1.1 Computing Environment

All statistical analyses will be performed using SAS[®] Version 9.4 or higher for Windows.

3.1.2 Sample Size Justification

This is an exploratory study. Sample size and power are not driven by hypothesis testing. Twelve to 15 subjects will be enrolled to receive PO administered belumosudil 200 mg BID.

3.1.3 General Considerations

General considerations for descriptive statistics, presentation, and analysis model (for efficacy analysis) used for continuous and categorical data are given below.

3.1.3.1 Continuous variables

Continuous variables will be described by using these descriptive statistics: number of observations (n), mean, standard deviation (SD), median, minimum and maximum.

The means, medians, and standard deviation (SD) will be reported to one decimal place more than the data reported on the case report form (CRF) or by the laboratory/vendor. Minimum and maximum will be reported to the same number of decimal places displayed on the CRF or by the laboratory/vendor.

3.1.4 Study Day

The study day for all assessments prior to the first study drug administration is calculated as the difference between the date of the event or measurement (e.g., adverse event [AE] onset date, assessment date, sample collection date, etc.) and the start date of study treatment. The day before the start of study treatment is Study Day -1.

The study day for all post assessments after the first study drug administration is calculated as the difference between the date of the event or measurement (e.g., AE onset date, assessment date, sample collection date, etc.) and the start date of study treatment plus one day. The first day of study treatment is Study Day 1.

3.1.5 Baseline

Baseline value is defined as the valid and last non-missing value obtained within 29 days prior to subject receiving the first study medication, unless otherwise stated under the related assessment section. Baseline can be the day before the first study medication or on the same day as the first study medication if a pre-dose assessment is available. Subjects without data on a parameter before the first study medication will have a missing baseline for this parameter.

3.1.6 Handling of Incomplete or Missing Data

There will be no imputation for missing efficacy values. Missing start and end dates for AE and concomitant medication (CM)

The assumption will be the worst or most conservative judgment when imputing AE and CM start and end dates. The purpose of imputing a start date is to help define whether the AE/CM started while taking study drug.

For a partial or missing start date:

- If the day is missing, the first day of the month will be imputed. If the missing day is the same as the month of first dose of study drug, then the first dose date will be imputed.
- If the day and month are missing, the first day of January will be imputed. If the year is the same as the first dose date, then the first dose date will be imputed.
- If the day is completely missing, the first dose date will be imputed. If the end date suggests it could have started prior to this, the first day of January of the same year as the end date will be imputed.
- When imputing a start date, the start date will ensure that the new imputed date is sensible, i.e., is prior to the end date of the AE or CM.

For a partial or missing end date:

- If the day is missing, the last day of the month or the last assessment date, whichever is earlier, will be imputed.
- If the day and month are missing, the 31st of December or the last assessment date, whichever is earlier, will be imputed.
- If the date is completely missing, there will be a need to look at whether the AE/CM is still ongoing before imputing a date. If the ongoing flag is missing, then it will be assumed that AE is still present, or CM is still being taken (i.e., do not impute a date). If the AE/CM has stopped, then the last assessment date will be imputed.

These data imputations are for categorization purpose only and will not be used in listings.

If the assessment of the relationship of the AE to belumosudil is missing, then it will be assumed that the AE is related to belumosudil and the AE considered as such in the frequency tables of possibly related AEs. No imputation should be done at the data level.

3.2 Analysis Populations

Three populations will be employed in the analysis of study data:

- The Modified Intent-to-treat (mITT) Population will consist of all subjects who receive at least 1 dose of belumosudil 200 mg.

- The Safety Population is defined as all subjects who receive at least 1 dose of belumosudil 200 mg. In this study, the Safety Population is equivalent to the mITT Population.

The primary endpoint will be analyzed on the modified Intent-to-Treat (mITT) Population.

Demographics, subject disposition, baseline characteristics, and efficacy analyses will be summarized in mITT Population and by group.

All safety analyses will be performed on the safety population.

3.3 Subject Disposition and Evaluability

A disposition of all enrolled subjects will be summarized. The number of subjects screening failed, discontinuing from study treatment, discontinuing from study and the primary reason for discontinuation will be summarized.

3.4 Protocol Deviations

All protocol deviations will be identified and classified as major or minor before the clinical database lock and will be presented in a listing.

Major Deviation: Protocol deviation that may impact the accuracy, and/or reliability of the study data or that may impact subject rights, safety or well-being.

Minor Deviation: Protocol deviation that does not impact the accuracy, and/or reliability of the study data or subject rights, safety or well-being.

3.5 Demographics and Baseline Characteristics

3.5.1 Demographics and Other Characteristics

A summary table and a by patient listing will be generated for patient demographics and other characteristics. Variables to be included are: age, sex, race, ethnicity, height, weight, child bearing potential, and other variables as applicable based on indication/study design.

Demographics and other baseline characteristics will be summarized in each population.

3.5.2 Medical History

Medical history will be summarized by primary system organ class (SOC) and preferred term (PT). Medical history will be coded using Medical Dictionary for Regulatory Activities (MedDRA, Version 22.0 or higher) terminology.

Medical history will be presented in a listing by patient and summarized in the Safety Population.

3.6 Concomitant Medications

Concomitant medications will be coded using World Health Organization (WHO) Drug Dictionary. Concomitant medications are all medications taken after the start of study consent, during the treatment period (day 1 until 28 days after last dose), including those started before but ongoing at the start of study treatment.

Concomitant medications will be summarized according to Anatomical Therapeutic Class (ATC) and preferred drug name.

Concomitant medications will be presented in a listing by patient and summarized in the Safety Population.

3.7 Treatment Compliance and Exposure

The relative dose intensity (RDI) will be used to assess the treatment compliance. The RDI is defined as:

$$RDI (\%) = 100 \times ADI (\text{mg/day}) / PDI (\text{mg/day}),$$

where ADI and PDI are the actual dose intensity and planned dose intensity, respectively:

$$PDI (\text{mg/day}) = \text{planned cumulative dose (mg)} / \text{duration of exposure (days)},$$

$$ADI (\text{mg/day}) = \text{actual cumulative dose (mg)} / \text{duration of exposure (days)}.$$

The planned cumulative dose is the planned daily dose amount multiplied by the duration of exposure, while the actual cumulative dose is the sum of actual total daily dose amount over the duration of exposure. The actual total daily dose will need the information of dose modifications (increased and reduced) and dose interruption (held) captured in CRF (Dose Modifications and Interruptions). If a subject does not take any study drug, the actual RDI by definition is zero.

The duration of exposure is defined as:

Duration of exposure (days) = (Date of last dose – Date of first dose) + 1, regardless of unplanned intermittent discontinuations.

One summary table will be generated for treatment exposure and compliance, including: treatment duration (weeks), treatment duration categories (0 to 12 weeks, 12 to 24 weeks, 24 to 28 weeks, 28 to 40 weeks, 40 to 52 weeks), actual cumulative dose, ADI, RDI, and RDI categories (>80%, <=80%; >95%, <=95%).

Another summary table will be generated for dose increased, dose reduced, dose held, and the reasons.

A by patient listing will be generated for the detailed exposure information.

It will be summarized in Safety Population and by group.

3.8 Definition of Efficacy Endpoints

3.8.1 Primary Efficacy Endpoint: CRISS

The primary efficacy endpoint is Combined Response Index in Diffuse Cutaneous Systemic Sclerosis (CRISS).

CRISS is a 2-step process for use in a clinical trial.

Step 1: patients who develop new onset of renal crisis, new onset or worsening of lung fibrosis, new onset of pulmonary arterial hypertension, new onset of left ventricular failure during the trial are considered as not improved and assigned a probability of improving equal to 0.0.

Step 2: For the remaining patients, step 2 involves computing the predicted probability of improving for each individual, using the equation shown below.

$$\frac{\exp[-5.54 - 0.81 * \Delta_{MRSS} + 0.21 * \Delta_{FVC\%} - 0.40 * \Delta_{Pt-glob} - 0.44 * \Delta_{MD-glob} - 3.41 * \Delta_{HAQ-DI}]}{1 + \exp[-5.54 - 0.81 * \Delta_{MRSS} + 0.21 * \Delta_{FVC\%} - 0.40 * \Delta_{Pt-glob} - 0.44 * \Delta_{MD-glob} - 3.41 * \Delta_{HAQ-DI}]}$$

where Δ_{MRSS} indicates the change in mRSS from baseline to follow up, $\Delta_{FVC\%}$ denotes the change in FVC% predicted from baseline to follow up, $\Delta_{Pt-glob}$ indicates the change in patient global assessment, $\Delta_{MD-glob}$ denotes the change in physician global assessment, and Δ_{HAQ-DI} is the change in HAQ-DI. All changes are absolute change (Time₂-Time_{baseline}).

As patient global assessment and physician global assessment are based on a VAS of 0 (Extremely Poor)-100 (Excellent) in CRF. When calculating the CRISS score, these 2 scores should be divided by 10 firstly to make it in a 0-10 scale.

The outcome is a continuous variable between 0.0 and 1.0 (0-100%). A higher score indicates greater probability of improvement. A CRISS score $\geq 20\%$ is considered as the minimal detectable difference and will be described as CRISS20 in the SAP. A CRISS score $\geq 60\%$ is considered as the minimally important difference and will be described as CRISS60 in the SAP. This will be the primary variable for efficacy.

Analysis of the primary efficacy endpoint will be conducted using the mITT population. The number and percentage of patients achieving CRISS60 response at week 24 will be summarized.

The following analysis on CRISS will also be provided as supportive evidence for the primary analysis.

- The number and percentage of patients who develop new onset of renal crisis, new onset or worsening of lung fibrosis, new onset of pulmonary arterial hypertension, new onset of left ventricular failure during the trial are considered as not improved and assigned a probability of improving equal to 0.0.
- The numerical CRISS Score at week 24.

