Study Objective(s)	
Primary Objective
 
The primary objective of this study is to evaluate the efficacy of belumosudil using the Combined Response Index in diffuse cutaneous Systemic Sclerosis (CRISS) at Week 24.
 
Secondary Objectives
 

• To assess CRISS at Weeks 8, 16, 36, and 52

• To evaluate the efficacy of belumosudil at Week 24 for:

○ Modified Rodnan Skin Score (mRSS)

○ Forced Vital Capacity (FVC)

○ Physician Global Assessment

○ Patient Global Assessment

○ Scleroderma Health Assessment Questionnaire—Disability Index (SHAQ-DI)

	

• To evaluate the efficacy of belumosudil at Weeks 8, 16, 36, and 52 compared to baseline for all subjects for the parameters in the bullet above

• To assess the safety of belumosudil in subjects with dcSSc by examining the percentage of subjects with treatment-emergent adverse events (CTCAE v5.0)

 
Exploratory Objectives
 

• [REDACTED]

[REDACTED]

[REDACTED]

[REDACTED]

[REDACTED]

[REDACTED]

[REDACTED]

Study Design	Phase 2, open-label, multicenter trial in subjects with dcSSc
Methodology	Subjects who have signed an Institutional Review Board/Independent Ethics Committee-approved informed consent form and met all of the inclusion/exclusion criteria will be enrolled. A total of 12-15 subjects will receive orally administered belumosudil 200 mg twice daily (BID) for 52 weeks. Study drug will be collected at the end of Week 52. The primary endpoint will be analyzed using Week 24 data. Efficacy will be assessed at baseline and throughout the 52 weeks of the treatment period using CRISS, mRSS, pulmonary function tests (PFTs), Physician Global Assessments, and Patient Global Assessments. Safety will be assessed throughout the study. Subjects will undergo evaluations as outlined in the Study Assessment table. A 4-Week Follow-Up visit will occur 28 days ( $\pm$ 3 days) after the last dose of study drug.
Approximate Number of Subjects	12 to 15 subjects will be enrolled.
Approximate Duration of Subject Participation	Approximately 14 months of study duration: 4-week screening period, 52-week treatment period, and 4-week follow-up

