2.2 Study Design

KD025-215/ACT17634 is a Phase 2, open-label, multicenter trial in subjects with dcSSc.

Subjects who have signed an Institutional Review Board/Independent Ethics Committee-approved informed consent form and met all of the inclusion/exclusion criteria will be enrolled. A total of 12-15 subjects will receive orally administered belumosudil 200 mg twice daily (BID) for 52 weeks. Study drug will be collected at the end of Week 52. The primary endpoint will be analyzed using Week 24 data.

Efficacy will be assessed at baseline and throughout the 52 weeks of the treatment period using CRISS, mRSS, pulmonary function tests (PFTs), Physician Global Assessments, and Patient Global Assessments. Safety will be assessed throughout the study.

Subjects will undergo evaluations as outlined in the Study Assessment table. A 4-Week Follow-Up visit will occur 28 days (\pm 3 days) after the last dose of study drug.

Efficacy will be assessed throughout the 52-week dosing period using CRISS, mRSS, PFTs, physician global assessment, SHAQ-DI.

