3.8.2 Secondary Efficacy Endpoints

3.8.2.1 CRISS

The numerical and categorical CRISS score will also be summarized for Weeks 8, 16, 36, and 52 on the mITT population.

3.8.2.2 mRSS

The mRSS is a measure of skin thickness rated with scores ranging from zero (0; normal) to three (3; severe skin thickening) across 17 different sites. The total score is the sum of the individual skin scores in the 17 body areas (e.g., face, hands, fingers; proximal area of the arms, distal area of the arms, thorax, abdomen; proximal area of the legs, and distal area of the legs, feet), giving a range of 0-51 units. A negative change from baseline demonstrates improvement.

MRSS total score, change from baseline, percent improvement will be summarized as a continuous endpoint at all scheduled assessment visits.

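### CRISS Step 1 has no cut-off at the visit being scored, so as written a first organ event after Week 24 sets the Week 24 primary score to 0.0

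*SAP*

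**What the plan says.** SAP 3.8.1 defines CRISS as a two-step score. Step 1 names new renal crisis, new or worsening lung fibrosis, new pulmonary arterial hypertension and new left ventricular failure. The rule closes with "new onset of left ventricular failure during the trial are considered as not improved and assigned a probability of improving equal to 0.0". Step 2 then covers everyone else: "For the remaining patients, step 2 involves computing the predicted probability of improving for each individual". The Step 2 equation uses changes from baseline to a follow-up time, so it can be computed visit by visit. Step 1 carries no such time reference.

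The primary summary is at one visit: "The number and percentage of patients achieving CRISS60 response at week 24 will be summarized". Two supportive analyses follow in the same section. One counts the Step 1 patients and repeats the open window ("during the trial are considered as not improved and assigned a probability of improving equal to 0.0"). The other is "The numerical CRISS Score at week 24". SAP 3.8.2.1 applies the same definition at four more visits: "The numerical and categorical CRISS score will also be summarized for Weeks 8, 16, 36, and 52 on the mITT population".

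On timing, the Protocol Synopsis (Methodology), Protocol 3.1 and SAP 2.2 all state: "The primary endpoint will be analyzed using Week 24 data". Protocol 6.1 likewise places the endpoint at the end of Week 24. Treatment lasts 52 weeks, and after the last dose "A 4-Week Follow-Up visit will occur 28 days" later (SAP 2.2). The protocol describes CRISS only as an algorithm and never mentions Step 1, so it supplies no event window either.

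**The concern.** A score labelled Week 24 should depend on what has happened to the patient by Week 24. As written, Step 1 makes it depend on the whole trial. A patient who meets CRISS60 at Week 24 and has a first listed event at, say, Week 40 is no longer among the patients passed to Step 2. The 0.0 then applies to Week 24 and also to Weeks 8, 16 and 36. Zeros at visits on or after the event are what the index intends; only visits before the event are affected.

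Two competent programmers could code this differently, one with a single flag per patient and the other with a flag per visit. Protocol 9.7.5 plans no interim analysis but allows one. Under the patient-level flag, an early look and the final analysis could report different Week 24 rates from identical Week 24 assessments.

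Late events are foreseeable from the documents themselves. Protocol 3.9 gives renal crisis and falls in FVC or DLco as examples of on-study progression. Protocol 1.1 puts interstitial lung disease at up to 60% of systemic sclerosis patients. In Protocol Appendix A, two of the three scheduled full lung-function time points after baseline (Week 52/EOT and follow-up) fall after Week 24 for a subject on schedule. No test is planned, but Protocol 9.7.1 says the study is mainly meant to guide later studies, and the Week 24 CRISS60 rate is its primary result.

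**Working it through.** The plan gives no figure to reproduce here: there is no power calculation and no expected event rate. The check has four parts.

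**1. Search for a cut-off.** SAP 3.8.1 and 3.8.2.1, and the CRISS text in the Protocol Synopsis and Protocol 6.1, 6.1.1 and 9.8.1, contain no sentence that limits Step 1 events to the visit being scored. The nearest text is the Week 24 data sentence. It does not mention Step 1, describes no data cut, and does not reach the other visits.

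**2. Length of the open window.** Visit days come from Protocol section 5 and Appendix A. Nominal last visit = Day 365 + 28 = Day 393, for a subject who completes; early discontinuers have a shorter window.

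| Visit scored | Day | Days from visit to Day 393 |
|---|---|---|
| Week 8 | 57 | 393 − 57 = 336 |
| Week 16 | 113 | 393 − 113 = 280 |
| Week 24 | 169 | 393 − 169 = 224 |
| Week 36 | 253 | 393 − 253 = 140 |
| Week 52 | 365 | 393 − 365 = 28 |

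From first dose (Day 1) to Day 393 is 392 days, and 224/392 = 57.1%. More than half of the window lies after the primary time point.

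**3. Weight of one affected responder.** Sample size is 12 to 15 (SAP 3.1.2).
- CRISS60 rate, all mITT subjects in the denominator: 1/15 = 6.7 points; 1/12 = 8.3 points. For example, 6/12 (50.0%) becomes 5/12 (41.7%), and 6/15 (40.0%) becomes 5/15 (33.3%).
- Mean Week 24 CRISS, where a responder's score of 0.60 to 1.0 becomes 0.0. With 15 subjects the mean falls by 0.60/15 = 0.040 to 1.0/15 = 0.067. With 12 it falls by 0.60/12 = 0.050 to 1.0/12 = 0.083. This assumes every subject has a Week 24 score.

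**4. How likely a late first event is, under assumed rates only.** Let p be the probability of a first Step 1 event between first dose and Day 393, with constant hazard and full follow-up. The probability that it falls after Week 24 is q = (1 − p)^(168/392) − (1 − p). The chance of at least one such patient among n is 1 − (1 − q)^n.

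| Assumed p | q | n = 12 | n = 15 |
|---|---|---|---|
| 0.05 | 0.0283 | 0.291 | 0.349 |
| 0.10 | 0.0558 | 0.498 | 0.578 |
| 0.20 | 0.1088 | 0.749 | 0.822 |
| 0.30 | 0.1582 | 0.873 | 0.925 |

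These are upper bounds on the chance that the CRISS60 rate changes, because not every patient with a late event would have been a Week 24 responder.

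**The case against.** The best case against is that the literal reading is strained. The open-ended phrase sits in a generic description of the index, while the trial-specific text fixes the time: Week 24 data, CRISS at the end of Week 24, and Step 2 changes measured from baseline to the scored time. An event after Week 24 is not Week 24 data, and a database cut at Week 24 would remove the problem for the primary endpoint. The impact is also unproven: a patient must respond at Week 24, then have a first listed event, and a programmer must apply it backwards. The 6.7 to 8.3 points is simply 1/n. Any error lowers response, so it cannot create a false efficacy signal.

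Much of this stands. The intent is probably a Week 24 limit, the number affected may be zero, and the probabilities in part 4 rest on assumed rates. The mean-score shifts also need their condition: SAP 3.1.6 imputes no missing efficacy values, so the mean may have fewer than 12 or 15 scores, and each patient would then weigh more. The planned Step 1 count would cap how many scores could be affected, though it does not separate early from late events.

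It does not settle the point. The operative scoring rule is the one in SAP 3.8.1, and the general sentence neither amends it nor covers Weeks 8, 16 and 36. No Week 24 data cut is specified. Being conservative is little defence where nothing is tested and the estimate itself is the product.

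**Conclusion.** The concern holds: the rule is wrong as written. It lets events after a visit determine that visit's score, including the primary Week 24 CRISS60 result, and it sits in conflict with the stated use of Week 24 data. For each Week 24 responder with a later first event, the effect is 6.7 points (n = 15) to 8.3 points (n = 12) on the primary rate. On the mean Week 24 score it is 0.040 to 0.083 across the two sample sizes. These figures assume all mITT subjects are in the denominator and, for the mean, that all have a Week 24 score. The direction is always downward. How many patients would be affected cannot be known from the documents. The correction should be made before the analysis is programmed, but the uncertainty over numbers and the likely intent keep this short of a critical defect.

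**What to change.** In SAP 3.8.1, state that for each scored visit Step 1 applies only to events with onset on or before that visit's CRISS assessments, and that the 0.0 then carries forward to all later visits. Count a lung-function test done inside its permitted window as part of the visit. For Week 24 that is Day 169 ± 7, or Day 162 to 176 (Protocol 5.2.8 and Appendix A, footnote C). Give the supportive count of Step 1 patients the same Week 24 limit, and report later events separately.

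The cost is one sentence in the SAP and a date condition in the program. The downside is that every Step 1 event needs an onset date. Protocol 9.3.4 already has onset dates recorded for adverse events, but the SAP does not say that Step 1 events are taken from those records, so the source should be named at the same time.

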## 6. EFFICACY AND SAFETY ASSESSMENTS

### 6.1 EFFICACY ENDPOINTS

Efficacy measurements will be performed as outlined in [Appendix A](#).

The primary efficacy endpoint is the effect of belumosudil 200 mg BID on the CRISS at the end of Week 24 in the mITT Population. The CRISS exponential algorithm determines the predicted probability of improvement from baseline, incorporating changes in mRSS, FVC% predicted, SHAQ-DI, and physician and Patient Global Assessments. The outcome is a continuous variable between 0.0 and 1.0 (0-100%). A higher score indicates greater probability of improvement. A CRISS score  $\geq 20\%$  is considered a clinically meaningful improvement. The calculation of CRISS will be performed from data available from the EDC and will not be performed by the investigator (or designee) on site.

Secondary efficacy endpoints include the change from baseline in mRSS, FVC, SHAQ-DI, Physician Global Assessment, and Patient Global Assessment.

Other efficacy outcomes include the change from baseline in mRSS for KD025-treated subjects. The mRSS is a measure of skin thickness rated with scores ranging from 0 (normal) to 3 (severe skin thickening) across 17 different sites. The total score is the sum of the individual skin scores in the 17 body areas (i.e., face, hands, fingers; proximal area of the arms, distal area of the arms, thorax, abdomen; proximal area of the legs, and distal area of the legs, feet), yielding a range of 0 to 51 units. The mRSS has been validated for patients with SSc. A negative change from baseline demonstrates improvement.

The effect of belumosudil will be explored for the change in baseline for SHAQ-DI, which assesses 5 scleroderma-specific Visual Analog Scale (VAS) items to explore the impact of participant's disease. Each VAS item will be rated separately in scale of 0 to 100 mm, with higher scores indicating more severe disease. The 5 items are: (1) intestinal disease, (2) breathing problem, (3) Raynaud syndrome, (4) finger ulcers, and (5) overall disease.

Onset/progression of ILD will be evaluated by the effect of belumosudil in the change in predicted FVC, which is based on institutional standards and will be measured as part of

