**How was your overall health during the last week?**

## 23. APPENDIX E: PATIENT GLOBAL ASSESSMENT

KD025  
Protocol Number KD025-215

IND 140383

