3.8.2.4 Physician Global Assessment

Physician global assessment is physician's assessment of patient's overall health during the last week based on a VAS of 0 (Extremely Poor)-100 (Excellent). A positive change from baseline demonstrates improvement.

Physician global assessment score, change from baseline, percent improvement will be summarized as a continuous endpoint at all scheduled assessment visits.

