3.8.2.6 Scleroderma Health Assessment Questionnaire-Disability Index (SHAQ-DI)

SHAQ-DI includes the general HAD-DI assessment and 6 scleroderma-specific Visual Analog Scale (VAS) items to explore the impact of participant's disease. The general HAD-DI assessment includes 8 sections: dressing, arising, eating, walking, hygiene, reach, grip, and activities. The 6 VAS items will be rated separately in scale of a 0–100 millimeters [mm], with higher scores indicating more severe disease. The 6 items are: 1) pain, 2) intestinal disease, 3)

breathing problem, 4) Raynaud syndrome, 5) finger ulcers, and 6) overall disease. A negative change from baseline demonstrates improvement.

SHAQ-DI total score, each of the 6 VAS scores and their change from baseline, percent improvement will be summarized as a continuous endpoint at all scheduled assessment visits.

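### As written, the CRISS rule in SAP 3.8.1 counts improvement in the patient or physician global against the patient

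*SAP*

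**What the plan says.** SAP 3.8.1 defines CRISS in two steps. Patients with specified new or worsening organ involvement are set to 0.0. For everyone else the score is exp(L)/(1 + exp(L)), where

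L = -5.54 - 0.81 x change in mRSS + 0.21 x change in FVC% - 0.40 x change in patient global - 0.44 x change in physician global - 3.41 x change in HAQ-DI.

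All changes are follow-up minus baseline. For the two globals the section states: "As patient global assessment and physician global assessment are based on a VAS of 0 (Extremely Poor)-100 (Excellent) in CRF". The preparation it orders is that "these 2 scores should be divided by 10 firstly to make it in a 0-10 scale". On the index itself it says: "A higher score indicates greater probability of improvement".

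SAP 3.8.2.4 (physician global) and 3.8.2.5 (patient global) repeat the same anchors, and each adds: "A positive change from baseline demonstrates improvement". For SHAQ-DI, section 3.8.2.6 gives the opposite direction: "A negative change from baseline demonstrates improvement".

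The primary analysis is the number and percentage of mITT patients reaching CRISS60 (a score of at least 60%) at Week 24. The numerical score and the Week 8, 16, 36 and 52 scores use the same rule. The protocol gives no equation. Its section 6.1 says: "The calculation of CRISS will be performed from data available from the EDC", and not by the investigator.

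**The concern.** With a negative coefficient, a component raises CRISS only if improvement is a negative change. That holds for mRSS and HAQ-DI. It fails for the two globals, which the SAP says improve upwards. Division by 10 changes the size of the global terms but not their sign.

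Read literally, the SAP rewards a patient whose globals get worse and penalises one whose globals get better. The error sits inside the formula for the primary variable and carries into every CRISS summary. It would tend to understate response if the drug improves the globals. The protocol says the study's main focus is to guide follow-up studies, so a distorted CRISS60 rate would mislead the decision it is meant to inform.

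**Working it through.** **Inputs from the SAP.** The coefficients, the definition of change, the 0 to 100 anchors and the division by 10 are in 3.8.1. The directions of improvement are in 3.8.1 and 3.8.2.2 to 3.8.2.6. The documents give no worked CRISS value to reproduce, so the equation is evaluated directly.

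**Sign check.**

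| Component | Coefficient | Change that means improvement | Effect of improvement on CRISS |
|---|---|---|---|
| mRSS | -0.81 | negative (3.8.2.2) | raises |
| FVC% predicted | +0.21 | positive (direction not stated; higher taken as better) | raises |
| HAQ-DI | -3.41 | negative (3.8.2.6) | raises |
| Patient global | -0.40 | positive (3.8.2.5) | **lowers** |
| Physician global | -0.44 | positive (3.8.2.4) | **lowers** |

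Only the two globals conflict with the stated direction of the index.

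**Size from the formula alone.** A 10 mm improvement is 1 unit after division by 10. If both globals improve by 10 mm:

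- As written, L falls by 0.40 + 0.44 = 0.84. Reversed, it rises by 0.84.
- The difference is 2 x 0.84 = 1.68 logits, and exp(1.68) = 5.37 on the odds scale.
- In mRSS points this is 1.68/0.81 = 2.07.

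**Effect on CRISS60.** The threshold is logit(0.60) = 0.405. With FVC% and HAQ-DI unchanged and both globals g mm better, the mRSS fall needed is (0.405 + 5.54 + 0.084g)/0.81 as written and (0.405 + 5.54 - 0.084g)/0.81 reversed. Rounded up to whole points:

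| Both globals better by | As written | Reversed |
|---|---|---|
| 0 mm | 7.34, so 8 | 7.34, so 8 |
| 10 mm | 8.38, so 9 | 6.30, so 7 |
| 20 mm | 9.41, so 10 | 5.27, so 6 |
| 30 mm | 10.45, so 11 | 4.23, so 5 |

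At 20 mm, a patient whose mRSS falls by 6 to 9 points is a non-responder as written and a responder with the globals reversed.

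**Two patients (assumed changes).**

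- mRSS -5, FVC% 0, HAQ-DI -0.25, both globals 15 mm better. As written, L = -5.54 + 4.05 + 0.8525 - 1.26 = -1.8975, CRISS 0.130. Reversed, L = 0.6225, CRISS 0.651. Not even CRISS20 becomes CRISS60.
- mRSS -4, FVC% 0, HAQ-DI 0, both globals 20 mm worse. As written, L = -5.54 + 3.24 + 1.68 = -0.62, CRISS 0.350. Reversed, L = -3.98, CRISS 0.018. Worsening globals create a CRISS20 response.

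**Group level, illustrative only.** None of these inputs comes from the documents. Improvement was simulated as multivariate normal (400,000 draws): mRSS mean 6, SD 6; FVC% mean 0, SD 6; HAQ-DI mean 0.2, SD 0.4; each global SD 20 mm, with its mean varied.

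| Correlation (all pairs) | Mean global improvement | CRISS60 as written | CRISS60 reversed | Reclassified |
|---|---|---|---|---|
| 0.4 | 0 mm | 47% | 48% | 12% |
| 0.4 | 10 mm | 41% | 52% | 15% |
| 0.4 | 20 mm | 35% | 57% | 23% |
| 0 | 0 mm | 47% | 47% | 14% |
| 0 | 10 mm | 41% | 53% | 18% |
| 0 | 20 mm | 35% | 59-60% | 26% |

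**Weight of one patient.** 100/15 = 6.7 and 100/12 = 8.3 percentage points.

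**The case against.** The strongest objection is that the documents prove a contradiction but not which side of it is wrong. Protocol Appendices D and E show the question, "How was your overall health during the last week", without readable anchors, and that question fits a scale running either way. If the form in fact runs from good to bad, dividing the raw value by 10 gives correct scores, no classification changes, and the error is confined to wording in 3.8.1, 3.8.2.4 and 3.8.2.5. This stands, and every size given here is conditional on the anchors being as stated. A missing reversal is the likelier explanation because 3.8.1 attributes the anchors to the CRF. The repetition in the two later sections adds less, since it may be copied text.

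Second, a programmer might notice the conflict and reverse the scale unprompted. That is possible, but the SAP says how to prepare these two scores and orders rescaling only. Because CRISS is calculated centrally, no site step would catch the error.

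Third, the harm is bounded. The SAP states that "Sample size and power are not driven by hypothesis testing", the analysis is descriptive, each global is also summarised separately in its stated direction, and CRISS can be recalculated from the raw data. All of this is true and limits lasting damage. It does not make the primary variable correctly specified.

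Finally, the worked patients and the simulation rest on assumed values. With no mean change in the globals the simulated CRISS60 rate hardly moves, and in every scenario most patients keep their class.

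**Conclusion.** The concern holds. The SAP's coefficients, definition of change, scale anchors and preparation step cannot all stand beside its statement that a higher CRISS means a greater probability of improvement. This follows from the SAP text alone.

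If the CRF anchors are as stated, every Step 2 score with a non-zero net weighted global change is wrong, by 1.68 logits per 10 mm change in both globals, and some CRISS20 and CRISS60 classifications flip. Patients set to 0.0 in Step 1, and those whose weighted global changes cancel, are unaffected. The shift in the overall CRISS60 rate depends on the mean global change, which is unknown. If the anchors are misdescribed, the CRISS scores are right but the SAP states the wrong direction of improvement for two secondary endpoints. Either way the text must be corrected before CRISS is programmed.

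**What to change.** 1. Check the anchors on the CRF for both globals.
2. If 0 is the worst and 100 the best state, replace the scaling sentence in SAP 3.8.1 with: *Before computing CRISS, each global is reversed and rescaled as (100 - VAS)/10; changes are then follow-up minus baseline.* Leave 3.8.2.4 and 3.8.2.5 on the original scale.
3. If the anchors run the other way, keep the division by 10 and correct the anchors and the direction of improvement in 3.8.1, 3.8.2.4 and 3.8.2.5.
4. In either case, add a program check on raw CRF values: moving each of the five components towards its confirmed better end, with the others held fixed, must raise CRISS.

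The cost is one look at the CRF, one SAP sentence (or corrected text in three sections), one line of code and the check. No new data are needed.
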